9.7 Intra-operative surgeon performance data collection

The following protocol will apply to all episodes of intra-operative performance data collection for StR's and Fellows. The intra-operative data collection for Consultant performed operations will differ slightly in that they require no supervision, and no surgeon will 'take over' the operation. However, the methods for recording the intra-operative data will remain the same.

A maximum of two study participants (excluding Consultants) will attend any given list. The PI ([name]) will attend the World Health Organisation (WHO) briefing in theatre on the morning of the list, introduce themselves and explain their role during the list. If recording an StR, neither the participant or PI will disclose which arm of the study the participants are in (routine training, or additional simulation training). The supervising Consultant will confirm the cases on the list the StR or AF's will be performing under supervision and training.

Operative protocol

After anaesthesia and patient set-up, the supervising Consultant and participant will scrub in up in the usual manner with the motion sensors in position on the lead surgeon's elbows under their sterile gown (see Appendix C). The procedure will then continue routinely and normally, but with the PI collecting motion data via the wireless Bluetooth sensors. The PI will also manually record the timings of each stage of the THR operation. This process will allow synchronisation of motion data to the participants progression throughout the stages of the operation. Data collection will stop when the dressing has been applied to the surgical wound.

Following completion of the operation, the participants in conjunction with the supervising Consultant will be asked to complete short written assessments of the lead surgeons' intra-operative performance. These assessments may include: Global Rating Scales (GRS), Objective Structured Assessment of Technical Skills (OSATS), and surgical checklists.

Intra-operative deviations or interruptions

Sometimes the supervising Consultant needs to take over part or all of an operation if it proves particularly difficult. In the event that a procedure has to be taken over completely by the Consultant then data recording will stop. If minor adjustments only are made by the Consultant during the operation then these will be noted and time marked against the motion data.

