3. SYNOPSIS

Study Title	A prospective randomised controlled study assessing the impact of simulation training in primary total hip replacement (THR).
Short title	THR Performance & Assessment
Study registration	IRAS Project ID: 270167 6th August 2019
Sponsor	University of Oxford/Clinical Trials and Research Governance Joint Research Office, [name]

Funder	Dinwoodie Charitable Company		
Study Design	Prospective randomised controlled study, with an additional comparator group.		
Study Participants	
Trauma & Orthopaedic Specialty Registrars (intervention and control groups), Consultant Orthopaedic Surgeons, and Arthroplasty Fellows.
 
Patients undergoing elective primary THR at the 2 named NHS Hospitals in this study, when their lead surgeon is enrolled as a participant in this study.
		
Participant Sample Size	
Surgeon participant Group 1 a: Interventional group ('StR's'): Thames Valley Deanery Trauma & Orthopaedic Specialty Registrars on Arthroplasty clinical placements (n=8) receiving additional training
 
Surgeon participant Group 1 b: control group (StR's): Thames Valley Deanery Trauma & Orthopaedic Specialty Registrars on Arthroplasty clinical placements receiving routine and normal Deanery training only (n=8).
 
Surgeon participant Group 2: ('Experts & Fellows'): Consultant Orthopaedic Surgeons (n=5), and nationally appointed Arthroplasty Fellows (n=8).
 
Patient Participants: Estimated total n= 193, calculated on the basis of outcomes data following THR to be collected for:
 
 8 patients per Specialty Registrar (n = 128) 5 patients per Fellow (n = 40) 5 patients per Consultant (n = 25) 		
Planned Study Period	
Total length of project = 18-24 months
 
Length of individual participants involvement = 6 months
		
Planned Recruitment period	
Start date for recruitment = August 2019
 
End date for recruitment = February 2021 (with possible extension to August 2021)
		
	Objectives	Outcome Measures	Timepoint(s)

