8.2. Patients

Adult patients (aged 18 years or above) diagnosed with primary hip osteoarthritis who have been listed for elective primary THR in the NHS.

Inclusion Criteria

- Adult patients (aged 18 years or above) diagnosed with primary hip osteoarthritis who have been listed for elective primary THR in the NHS.
- THR operation performed by a surgeon participant as lead surgeon.

Exclusion Criteria

Patients may not enter the study if ANY of the following apply:

- Patients with complex hip pathology (e.g. previous trauma, hip dysplasia, infection).
- Patients who have had previous surgery on their affected hip.

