11 STATISTICS AND ANALYSIS

Analysis of motion data.

Motion data from the wireless sensors produces performance surrogate markers such as: the number of movements (major & minor); total path length; and smoothness/economy of movement. Data distributions will be assessed for normality using the Shapiro-Wilk test. Previous studies show such data are not normally distributed, and we would expect to use non-parametric tests, such as the Mann-Whitney U test to compare the performance metrics between the 2 groups of participants (StR's against Experts & Fellows). The Mann-Whitney U test will also be used to compare performance metrics between the two sub-groups of StR's (control and intervention), and also within the intervention sub-group in order to compare performance before and after training.

Performance metrics within all groups of participants will be reported using descriptive statistics to outline the central tendency (mean, median, and mode) and variation (range, variance, and standard deviation) in readings obtained. The Kruskal-Wallis one-way analysis of variance (ANOVA) test will be used to test for differences in the mean values obtained for all performance metrics between the two groups of participants. The Wilcoxon signed-rank test will be used to determine any differences in performance metric between the two groups.

Analysis of other routinely obtained data

X-ray (radiograph) analysis:

X-rays will be reviewed by two independent Consultant Orthopaedic Surgeons who will be blinded to the patient and lead surgeon's identity in order to reduce bias. There are several important parameters to be evaluated when reviewing a pelvic x-ray, therefore we will ask each reviewer to allocate a categorical global rating (see below) for both the pre- and post-operative x-rays. [5] The Chi-squared test will be used

to determine if there are any significant differences between each group, and also intra-group differences (for example StR's before and after additional training).

Pre-operative x-ray

- 1: Hip osteoarthritis without significant bone loss.
- 2a: Hip osteoarthritis with significant bone loss on acetabular side.
- 2b: Hip osteoarthritis with significant bone loss on femoral side.
- 3: Hip osteoarthritis with significant bone loss on both acetabular and femoral sides.

Post-operative x-ray

- 1: Excellent implant position and restoration of hip anatomy.
- 2a): Good overall with minor imperfections on acetabular side.

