12 DATA MANAGEMENT

Within this study both patients and participants will have all of their personal data anonymised via the use of Unique Patient or Participant Identifiers (UPI's). A master list of key linking identifiers for both patients

and participants will be kept on a password protected file on the OUH secure Trust Network Server. Only completely anonymised data will be used outside of OUH Trust property, which will be kept on a password-protected University owned laptop or hard-drive. We plan on keeping study data for a period of 5 years following completion on the study (up to December 2026), before securely disposing of it. We believe that this storage is appropriate as the core content is scientific research data and is therefore in the public interest. Furthermore, we will require access to this data in the case of individuals wishing to scrutinise the scientific methodology, results, or conclusions of our study.

Intra-Operative Data

Raw data will be produced from the wireless sensors. Please see section 12.3 for further details regarding the recording, transfer, and storage of this data.

Other 'personal data'

1) Electronic Patient Record Data

The following data will be obtained from the NHS Electronic Patient Records (EPR), which includes the Insignia Picture Archiving and Communication System (PACS), and the Theatre Management System (TMS):

- X-ray (radiograph) analysis.
- Theatre time usage.
- Blood test & transfusion rate analysis.
- Peri-operative morbidity (30 day).
- In-patient length of stay.
- Patient demographics (age, gender, BMI)

2) Questionnaire Data

Patient Questionnaire Data

The patient questionnaires consist of the following components:

- Patient Reported Outcome Measures: The OHS and EQ-5D.

Participant (Medical Health Professionals) Questionnaire Data

Written assessments of intra-operative performance will be conducted shortly after completion of a recorded THR. These assessments may include: Global Rating Scales (GRS), Objective Structured Assessment of Technical Skills (OSATS), and surgical checklists. The data collected from these will be anonymised as it will be linked with the UPI, and not provide any names or other personal information. The hard copies will be transcribed into digital format as soon as possible, which will be stored onto a password protected encrypted file on a University owned computer/hard-drive. The hard copies of the forms will then be disposed of.

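### The StR v Experts & Fellows comparisons are non-randomised, yet they are not adjusted for the pre-operative x-ray grade, BMI or age that the trial already collects

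*Combined protocol and SAP*

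**What the plan says.** **Who belongs to which group.** One inclusion criterion in section 8.2 is "THR operation performed by a surgeon participant as lead surgeon", so a case counts towards StRs or Group 2 according to who led it. Section 9.7 adds: "The supervising Consultant will confirm the cases on the list the StR or AF's will be performing under supervision and training". AF's are the Arthroplasty Fellows, who sit in Group 2 with the Consultants. No criterion for this confirmation is given.

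**Which hips are eligible.** Section 8.2 admits primary hip osteoarthritis. It excludes complex pathology, with trauma, dysplasia and infection as examples, and any earlier operation on that hip. Bone loss is not named. In section 11, two Consultants blinded to patient and lead surgeon are each asked to "allocate a categorical global rating (see below) for both the pre- and post-operative x-rays". Three of the four pre-operative categories (2a, 2b and 3) describe significant bone loss.

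**How the groups are compared.** Section 11 names the Mann-Whitney U test for motion metrics, similar methods for cup inclination and version, and a t-test or Mann-Whitney U test for theatre time, blood loss and other continuous outcomes. The x-ray categories are compared between groups by chi-squared. No stratification, covariate, matching or restriction appears.

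**What is collected.** Section 12 lists "Patient demographics (age, gender, BMI" among the items taken from the patient record.

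**Planned cases.** The synopsis gives "Estimated total n= 193", made up of "8 patients per Specialty Registrar (n = 128", "5 patients per Fellow (n = 40" and "5 patients per Consultant (n = 25".

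**The concern.** Only the two StR arms are randomised. Between StRs and Group 2, the patient's surgeon is settled within routine care, and nothing in the plan makes that choice independent of how hard the hip is. If bone loss affects time, movements, blood loss or cup position, and is unevenly spread between the groups, an unadjusted comparison mixes experience with case mix.

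Two uses of the data are exposed, by different routes. The first is the part of the secondary objective that asks whether performance metrics relate to surgical experience; this rests on the StR v Group 2 comparison. The second is the expert standard. It comes from Group 2's own cases, and section 5 intends it as a benchmark for trainees, so it carries whatever mix of hips those cases happened to have.

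**Working it through.** **1. The plan's own figure.** 16 × 8 + 8 × 5 + 5 × 5 = 128 + 40 + 25 = 193, as stated. Group 2 contributes 40 + 25 = 65 cases, so the comparison is 128 v 65. At the lower recruitment figures in section 8.1 (12 StRs, 6 Fellows) with 5 Consultants, it is 12 × 8 = 96 v 30 + 25 = 55, a total of 151. The documents give no SD, effect size, significance level or grade distribution, so every input below on bone loss is an assumption.

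**2. Size of the bias.** Let p1 and p2 be the shares of bone-loss hips among StR and Group 2 cases, and δ the shift in a metric due to bone loss. With no experience effect, the expected difference in means, Group 2 minus StR, is (p2 − p1) × δ. Example: (0.30 − 0.10) × 1 SD = 0.20 SD. Reversing the shares reverses the sign.

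**3. Effect on the planned test.** The simulation used 128 v 65 cases, a normal outcome with SD 1, no experience effect, two-sided 0.05 (assumed) and 4,000 runs per setting. Monte Carlo error is about √(0.05 × 0.95 / 4,000) = 0.3 percentage points near 5%. The stratified test is a van Elteren rank test by grade (bone loss or none).

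| Bone loss, StR v Group 2 | δ (SD) | Bias (SD) | Mann-Whitney rejects | Stratified rejects |
|---|---|---|---|---|
| 20% v 20% | 0.5 | 0 | 4.7% | 4.9% |
| 20% v 20% | 1 | 0 | 4.5% | 4.2% |
| 10% v 20% | 0.5 | 0.05 | 6.5% | 5.2% |
| 10% v 20% | 1 | 0.10 | 9.0% | 4.7% |
| 10% v 30% | 0.5 | 0.10 | 10.4% | 5.5% |
| 10% v 30% | 1 | 0.20 | 22.1% | 5.6% |
| 10% v 40% | 0.5 | 0.15 | 15.4% | 5.0% |
| 10% v 40% | 1 | 0.30 | 41.9% | 5.1% |
| 5% v 40% | 0.5 | 0.175 | 18.6% | 4.0% |
| 5% v 40% | 1 | 0.35 | 56.0% | 4.8% |

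Two limits apply. Cases are treated as independent, although they are nested within surgeons. Stratification restores about 5% because grade is the only case-mix difference built in and is read without error; real adjustment would be partial.

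**4. Dilution by Fellows.** Fellows' cases are confirmed in the same way as StRs' cases. If an excess e of bone-loss hips exists only among Consultants' own cases, and Fellows' cases resemble StRs', the Group 2 excess is (25/65) × e = 0.385e. For e of 10 to 30 points this is 3.8 to 11.5 points, and with δ of 0.5 to 1 SD the bias is 0.02 to 0.12 SD. The upper end lies just beyond the 10% v 20%, 1 SD row. At the lower recruitment figures the fraction is 25/55 = 45%.

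**5. The benchmark.** If a share q of Group 2 hips has bone loss, the Group 2 mean differs from its mean for grade 1 hips by q × δ. With q of 10% to 40% and δ of 0.5 to 1 SD, that is 0.05 to 0.40 SD.

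**6. Does the chi-squared test on grade deal with this?** With 128 v 65 cases and grade taken as bone loss or none, its power is about 49% for 10% v 20% and 92% for 10% v 30%. It may reveal an imbalance, but no step follows from the result and the other comparisons stay unadjusted.

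**The case against.** The case against has real force on several counts.

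- **The grade is not ignored.** It is compared between groups, so a marked imbalance would probably be seen. That stands. The gap is that the performance and outcome comparisons are not adjusted for it.
- **Direction is open.** A reader might infer that case selection would be mistaken for an effect of experience. The documents do not support so definite a reading. If Consultants led the harder hips and those hips took longer, a true trainee-expert gap would be masked. The opposite mix would exaggerate it.
- **Confirming is not choosing.** A reader might infer that Consultants keep difficult hips for themselves. Section 9.7 says only that they confirm cases, for Fellows as well as StRs. The direct Consultant route covers 25 of the 65 Group 2 cases.
- **Bone loss may be partly excluded.** The list of complex pathologies is open-ended and could be read to cover some of it. The grading scale suggests that such hips are expected, but this is an inference.
- **Not every objective rests on this comparison.** A reader might infer that both secondary objectives do. The expert standard uses Group 2's own data, and relating metrics to patient outcomes is a different question.
- **The randomised StR comparison is not challenged.** Section 9.7 also keeps the arm undisclosed at the list.

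What remains is that the StR v Group 2 comparison is non-randomised, a blinded pre-operative measure related to difficulty is in hand, and section 11 leaves it out of the comparisons where it would help.

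**Conclusion.** The point holds as a gap in the analysis plan for the StR v Experts & Fellows comparisons. Case mix may differ between the groups, and the planned tests cannot separate that from experience. The bias could run either way and could be nil. The expert benchmark may also shift with the hips that Group 2 happens to operate on.

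No size can be derived from the documents. Over the unequal mixes tried, the unadjusted false-positive rate ran from 6.5% to 56.0%; with equal mixes it stayed near 5%. If only the Consultants' own cases differ by 10 to 30 points, the bias is about 0.02 to 0.12 SD. These figures rest on assumed bone-loss shares and shifts and on independent cases, so they show what is possible, not what is likely. The change is worth making because it uses data already collected and costs almost nothing.

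**What to change.** In section 11:

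- Pre-specify that the StR v Group 2 comparisons are stratified by or adjusted for blinded pre-operative grade (1 v 2a/2b/3), BMI and age. A regression of the metric, transformed if needed, on group and these three variables would serve; a grade-stratified rank test is an alternative for grade alone.
- State how one grade is reached when the two reviewers disagree. Section 11 gives no rule.
- Report the expert standard overall and by grade, with grade 1 hips only as a sensitivity analysis. Making grade 1 the main analysis would change the target population and shrink a group of 65 cases from 13 surgeons.
- Tabulate grade, BMI and age separately for StRs, Fellows and Consultants.
- State as limitations what adjustment leaves behind. Consultants come only from the NOC while StRs come from both hospitals (8.1), and recording stops when a Consultant takes over a case completely (9.7).

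No new data are needed. The cost is slightly more analysis work and thin higher-grade strata. At an assumed 10% of StR and 20% of Group 2 cases, there would be about 13 bone-loss hips on each side (0.10 × 128 = 12.8; 0.20 × 65 = 13), and only 5 among Consultants at 20% (0.20 × 25). That is why grades 2a, 2b and 3 are combined. Clustering of cases within surgeon is a separate matter that this change does not settle.

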9.8 Protocol Early Discontinuation/Withdrawal of Participants

During the course of this study a participant or patient may choose to voluntarily withdraw early at any time. This may happen for several reasons, including but not limited to:

- Inability to comply with study procedures or timetable.
- Participant or patient decision.
- Moving outside of the area.

Patients or participants may choose to stop study assessments. Patients or participants may also withdraw their consent, meaning that they wish to withdraw from the study completely. Patients who withdraw from this study will continue to receive routine clinical care under their named Consultant on the NHS.

According to the design of the study, the Investigator may discontinue a patient or participant from the study treatment at any time if the Investigator considers it necessary for any reason including, but not limited to:

- Ineligibility (either arising during the study or retrospectively having been overlooked at screening).
- Significant protocol deviation.
- Significant non-compliance with intervention (simulation training) or study requirements.
- Clinical care decision.

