7. STUDY DESIGN

Please see Appendix A for study flow diagram.

This is a prospective randomised controlled study designed to assess the impact of specific training interventions on surgical trainee's operative performance and patient outcomes following primary elective THR. We will also study the performance and patient outcomes of both 'Experts' and 'Fellows' in an additional comparator group, which will allow a potential expert standard in THR to be defined.

All study participants will be recruited from 2 Hospitals within the Thames Valley (Oxford) Post-graduate Medical Deanery, and will be composed of: Trauma & Orthopaedic Specialty Registrars ('StRs') holding national training numbers; Consultant Orthopaedic Surgeons ('Experts'); and Orthopaedic Arthroplasty Fellows ('Fellows'). Over the 18-24 month anticipated study period we aim on recruiting a total of up to 16 StR's, 8 Fellows, and 5 Experts. See section 9 for further details on participant recruitment.

StR's will be randomised in a 1:1 ratio to receive either: routine normal Deanery training (the control group, n=8); or routine normal Deanery training with additional simulation-based and cognitive learning (the intervention group, n=8). The intervention group will receive this training for 1-2 hours per week over a 4 to 6-week period. The 'Experts' and 'Fellows' will not be eligible for any intervention, and will act as a separate comparator group.

All participants will be assessed intra-operatively at set timepoints when performing elective primary THR surgery on patients within the named NHS Hospitals. The timepoints will vary depending upon each group. Each StR enrolled into this study will be assessed at a minimum of 8 separate THR operations over a 6-month period, commencing at 6 weeks in to their 6-month clinical placement. Both the 'Fellows' and 'Experts' will be assessed at a minimum of 5 separate THR operations depending upon the reliability of their performance data.

All patients in this study will have been listed for routine elective primary THR surgery under a named Orthopaedic Consultant on the NHS. There will be no interventions or deviations from routine clinical practise regarding the pre-operative investigations or work-up, the operation itself, the peri-operative care, or post-discharge follow-up.

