8. PARTICIPANT & PATIENT IDENTIFICATION

8.1. Consultants, Fellows, and Specialty Registrars

Group 1 ('StR's'): Trauma & Orthopaedic Specialty Registrars on Arthroplasty clinical placements.

Group 2 ('Experts' and 'Fellows'): Consultant Orthopaedic Surgeons, and nationally appointed Orthopaedic Arthroplasty Fellows.

Inclusion Criteria

Group 1 ('StR's'): All Specialty Registrars holding a National Training Numbers (NTN) in Trauma & Orthopaedic Surgery within the Thames Valley (Oxford) Deanery and who are or will be working on arthroplasty clinical placements at either the NOC, Oxford University Hospitals NHS Foundation Trust, or WGH, Buckinghamshire Healthcare NHS Trust over the specified recruitment period will be eligible for participation in this study. We anticipate recruiting 2 StR's from each recruitment centre every 6 months, over an 18 to 24-month period (total n = 12-16).

Group 2 ('Experts' and 'Fellows'): All Consultant Orthopaedic Surgeons with a sub-specialty practise in adult reconstructive (arthroplasty) surgery holding substantive posts at the NOC are eligible for participation in this study. The Consultant Orthopaedic Surgeons at WGH will not be required for the intra-operative assessment within this study, as we will gather sufficient motion data from the NOC Consultants to be able to benchmark an 'expert' performance. Nationally appointed Orthopaedic AF's working at either at either the NOC, Oxford University Hospitals NHS Foundation Trust, or WGH, Buckinghamshire Healthcare NHS Trust over the specified recruitment period will be eligible for participation in this study. We anticipate recruiting 2 AF's every 6-months over an 18 to 24-month period (total n = 6-8)

Exclusion Criteria

- Inability to comply with study procedures or timetable

- Moving outside of the area, relinquishing their position, or National Training Number.

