9.3. Subsequent Visits

Group 1a ('StR's') - Intervention group:

StR's randomised to the 'intervention group' will be required to complete the 4-week period of additional training outlined in section 9.3. Following completion of this additional training, participants within this group will undertake approximately 2 intra-operative assessments every 6 weeks over the duration of their 6-month clinical placements (total 8 assessments). The StR's will also undertake a final Technical Skills assessment in OOSEC Laboratory at 3 months into their placement (See Appendix A for Study Flow Diagram).

Group 1b ('StR's') – control group:

Participants within this group will undertake approximately 2 intra-operative assessments every 6 weeks over the duration of their 6-month clinical placements (total 8 assessments). The StR's will also undertake a final Technical Skills assessment in OOSEC Laboratory at 3 months into their placement (See Appendix A for Study Flow Diagram).

Group 2: 'Experts' and 'Fellows':

Following enrolment for participation in this study, all participants within this group will undergo a baseline practical skills assessment within the OOSEC. Participants within this group will then undertake a minimum of 5 separate intra-operative assessments each.

Patients:

Following enrolment for participation in this study, all patients will be asked to complete the pre-operative PROMs questionnaires (EQ-5D and OHS). These are part of routine clinical care, and are a mandatory for all patients undergoing THR in the NHS. The patients will not be asked to undertake any further assessments outside of their routine clinical care until the time of their scheduled post-operative out-patient department (OPD) clinic review appointment. All patients will only be followed up routinely following discharge by their named Consultant in an OPD clinic. This OPD appointment normally takes place 6 to 8 weeks following discharge. No additional clinic appointments or investigations will be required outside of the patients expected routine clinical care. At this visit the patients will be asked to complete the post-operative validated PROMs questionnaires (EQ-5D and OHS). This takes a few minutes and is the only extra outcome measure the patients are asked to complete.

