9.5 Blinding and code-breaking

Standard surgical practise will be followed. Patients are not formally blinded to which Surgeon (Consultant, Fellow, or StR) performs their operation, and are informed if requested. In line with standard surgical practise and training within the NHS, patients will provide informed consent that they understand no guarantees can be given that a particular person will perform the procedure. The person will, however, have appropriate experience.

Due to the nature of this study the StR's cannot be blinded to their allocations into either the 'control' or 'intervention' groups, however the assessment methods and any assessors will be blinded.

9.6 Description of study intervention(s),

The intervention to be tested is the simulation-based and cognitive learning package, which will be delivered to a randomised sub-group of 50% of the StR's recruited into this study. This will be delivered in a supervised setting within the OOSEC over a 4-week period for between 1 to 2 hours per week, over 3 to 4 consecutive but separate six-month placements (please see Appendix A for Study Flow Diagram). This will take place on a Wednesday afternoon, which is when all the Regional StR's are due to attend teaching in Oxford at the NOC.

The OOSEC is a secure enclosed laboratory space within the NOC, which contains all the necessary equipment required to run the simulation-based and cognitive learning training. The simulation training in general may include:

- 1) Focussed workshops on saw-bone models (simulated bones)
- 2) Digital and computer-based cognitive learning packages
- 3) Virtual reality platforms.

All participants within group 1 (StR's) will be asked to attend and complete baseline and final assessments within the OOSEC, which will consist of a multiple-choice questionnaire (MCQ) and a simulated procedure. Participants within group 2 (Consultants and Fellows) will only be required to complete a baseline simulated procedure.

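### A discontinuation ground that only the intervention arm can meet, with no statement that StRs taken off training are still assessed and analysed as randomised

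*Combined protocol and SAP*

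**What the plan says.** - **Discontinuation (9.8).** The power is broad: "the Investigator may discontinue a patient or participant from the study treatment at any time". One listed reason is "Significant non-compliance with intervention (simulation training) or study requirements". What counts as significant is not defined. Separately, 9.8 lets a participant choose to stop assessments or to withdraw consent altogether.
- **Who has the training (9.6 and 7).** The package is "delivered to a randomised sub-group of 50% of the StR's recruited into this study". The other half receive routine Deanery training.
- **Who knows the arm (9.5 and 9.7).** Section 9.5 says that StRs cannot be blinded, "however the assessment methods and any assessors will be blinded". Section 9.7 adds that in theatre "neither the participant or PI will disclose which arm of the study the participants are in".
- **When assessment starts.** For the intervention arm, 9.3 reads: "Following completion of this additional training, participants within this group will undertake approximately 2 intra-operative assessments every 6 weeks". The matching paragraph for controls has no such lead-in. The lay summary (section 2) also starts trainee outcome measures after simulation training, where that applies. Section 7 instead says that each enrolled StR is assessed at no fewer than 8 operations, starting six weeks into the placement.
- **Analysis (11).** Control and intervention StRs are compared by Mann-Whitney U test. Section 11 names no analysis population and gives no rule for StRs who stop training or miss assessments.

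**The concern.** The randomised comparison rests on very few surgeons: "StR's will be randomised in a 1:1 ratio to receive either" routine or additional training, 8 per arm. A control StR cannot fail to attend simulation training, so any loss on that ground falls on the intervention arm alone. The decision is made by someone who must know the arm, against an undefined threshold, and section 13.6 provides no oversight committee.

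If assessment begins only once training is complete, a StR taken off training may contribute no operations. The intervention arm would then consist of those who finished, compared with an unselected control arm. If those who do not finish also tend to be the weaker operators, simulation would look better than it is. If the StRs who miss sessions are the stronger or busier ones, the bias would run the other way. The documents do not indicate which is likelier.

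**Working it through.** **1. The start rules side by side.** Section 7 sets a calendar start (week 6) for every enrolled StR. Section 9.3 and the lay summary set an event start (training completed) for the intervention arm. Training lasts 4 weeks (9.6) or 4 to 6 weeks (7), so the two rules can agree for a StR who begins training with the placement and finishes on time. They part for a StR who does not finish: section 7 implies assessment from week 6, while 9.3 read literally never starts it. Neither mentions a discontinued StR.

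**2. Is the decision-maker unblinded?** This is inferred. The PI is told not to disclose the arm, which presupposes knowing it, and nobody can judge compliance with training without knowing who was assigned to it. The blinding claim in 9.5 covers assessment methods and assessors only.

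**3. The plan's own figure.** Patients: 16 × 8 + 8 × 5 + 5 × 5 = 128 + 40 + 25 = 193, as in the synopsis. This is a headcount. The documents give no SD, effect size, alpha, power or expected non-compliance, so there is no power figure to reproduce.

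**4. What each loss removes.** With 8 StRs per arm and 8 patients each, an arm has 64 patients.
- One loss: 1/8 = 12.5% of the arm's surgeons, leaving 56 v 64 patients.
- Two losses: 48 v 64 patients.
- With 6 per arm (the low end in 9.4), one loss is 1/6 = 16.7% of the surgeons, leaving 40 v 48 patients.

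**5. Shift in the arm mean with no true effect (assumed inputs).** Take one normally distributed score per StR with SD 1, and a compliance score correlated ρ with performance. Remove the k least compliant of n intervention StRs. The expected shift is

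shift = −ρ × (sum of the expected values of the k lowest of n standard normal scores) / (n − k).

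For n = 8 the two lowest expected values are −1.424 and −0.852.
- k = 1: 1.424/7 = 0.203 SD at ρ = 1; half of that, 0.10 SD, at ρ = 0.5.
- k = 2: (1.424 + 0.852)/6 = 0.379 SD at ρ = 1; 0.19 SD at ρ = 0.5.
- ρ = 0: no shift.

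With n = 6 and ρ = 1 the shifts are about 0.25 SD (k = 1) and 0.48 SD (k = 2).

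**6. False-positive rate.** Simulation under no effect, 8 StRs per arm before losses, at least 20,000 runs per scenario, exact two-sided Mann-Whitney test at 0.05 with the StR as the unit. Ranges are across repeated runs.

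| StRs lost | ρ = 0 | ρ = 0.5 | ρ = 1 |
|---|---|---|---|
| 1 | about 4% | 4.4-4.5% | 6.1-6.3% |
| 2 | about 4% | 5.5-5.8% | 10.5-11.0% |

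With nobody lost the rate is about 5%. The ρ = 0 column is lower because the exact test is coarser at unequal small sizes (4.0% at 7 v 8, 4.3% at 6 v 8). At ρ = 0.7 with two lost, the rate is about 7%. At ρ = 1, false findings in favour of training alone rise from about 2.4% to about 5% (one lost) or 10% (two lost).

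**The case against.** The strongest reply is that the protocol does not order anyone's removal. The Investigator's power in 9.8 is worded as discontinuation from study treatment, and 9.8 treats stopping assessments and withdrawing consent as the participant's own choices. Section 7 promises assessment of every enrolled StR from a calendar date, and section 6 collects outcomes for patients of any participant. On this view the lead-in in 9.3 only describes the expected sequence of visits.

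Much of this stands. A reader might infer that nothing keeps these StRs in the comparison, or that the plan excludes them by rule. The documents do not support that: section 7 points the other way, and any exclusion is permitted by silence. The reply still does not settle the matter. Section 7 does not address a discontinued StR, and it conflicts with 9.3 and the lay summary for anyone who does not finish training. Nor can the term study treatment be confined to simulation training, because 9.8 applies it to patients too, and they receive no study intervention.

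Two further limits are accepted. The same bullet also names study requirements, which bind both arms, so only its training limb is one-sided. Removals may also be rare: training is 1 to 2 hours a week, on an afternoon when StRs are already due at teaching (9.6).

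**Conclusion.** The point holds as a gap that can act on one arm. Sections 9.8, 9.3 and 11 together allow intervention StRs who do not complete training to be lost from the randomised comparison, and section 7 does not clearly prevent it. The bias would favour simulation only if non-compliance goes with poorer performance.

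The size is illustrative: about 0.10 to 0.20 SD for one loss in eight, and 0.19 to 0.38 SD for two, over correlations of 0.5 to 1. It rests on an assumed correlation, an assumed number of losses, normal scores and one score per StR, none of which the documents supply. It would be tempting to put the 10-11% false-positive rate first. That figure needs a quarter of the arm lost and perfect correlation; at a correlation of 0.5 the rate stays near 5%. The case rests on a directional bias and on losing the comparison as randomised, in a trial with at most 8 surgeons per arm. It should be corrected, and correcting it is nearly free.

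**What to change.** 1. **Sections 2 and 9.3.** Reconcile with section 7, so that intra-operative assessments in both arms start at the same calendar point in the placement, whatever training was attended.
2. **Section 9.8.** State that discontinuation from training is recorded by arm with its reason, and does not end outcome collection unless the StR chooses to stop assessments or withdraws consent. Both of those choices already exist in 9.8 and should be kept.
3. **Section 11.** State that all randomised StRs, and their patients, are analysed in the arm assigned. A compliers-only comparison can be given as a sensitivity analysis.

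The cost is a few sentences. There are no visits beyond those planned, and the planned 8 v 8 StRs and 64 v 64 patients are unchanged. The small downside is that the estimate will include StRs who had little training.
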